## **12.0 Potential Benefits to Subjects and Others**

### **12.1 Potential Benefits to Subjects**

None

### **12.2 Potential Benefits to Others**

The results of this study will be used determine whether methohexitol is a safer drug to use in anesthetic induction of patients receiving ACEI or ARBs (by causing less hypotension and less administration of vasopressor drugs). If this is the case, it may contribute to changing standard anesthetic practice and improving patient safety.

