## **3.3 Early Withdrawal of Subjects**

### **3.3.1 Criteria for removal from study**

1. Unanticipated difficult airway
2. Unanticipated arrhythmia occurring during or immediately following anesthetic induction
3. Unanticipated adverse effect of pre-induction drugs (lidocaine, fentanyl) or induction drugs (methohexitol or propofol).

4. Non-adherence to study protocol guidelines for practical reasons or safety reasons

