### **10.3 Method of collection of safety information**

Any adverse effects believed to be related to the administration of study drug (as determined by anesthesiologist co-investigators in this study) will be recorded on a case report form and submitted to the PI of the study within 24 hours of occurrence.

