#### **10.7 Statistical tests**

Not applicable, due to the established safety of the study drugs compared to the study population size.

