### **11.0 Risks**

The research requires the establishment of a second intravenous line following anesthetic induction. The use of an additional intravenous line is common anesthetic practice, although (as with any invasive procedure) there is the risk of bleeding, infection at the venipuncture site and infiltration of the intravenous catheter with the infusion of medications or fluids. In this study, the line will be used to draw blood samples, but following termination of the study protocol it will be used for the administration of standard fluids and drugs required for anesthetic care.

While there is currently no evidence to suggest that either randomization arm is harmful compared to the other, there is the risk that patients will be randomized to receive an induction drug that may potentially cause more hypotension compared to the other. We will perform interim analysis of our data and stop the study should we have reason to believe that one medication is causing significant harm compared to the other. Patients will be randomized to receive either propofol or methohexitol which both have the potential to cause hypotension.

Risks of propofol:

>10% incidence: low blood pressure (3%-26%), Injection site burning, stinging, or pain (18%), stop breathing for 30-60 seconds (adults 24%)

1% to 10% incidence: abnormal heart rhythm (1% to 3%), slow or fast heart rate (1% to 3%), cardiac output (volume of blood pumped by the heart per minute) decreased (1% to 3%);

Risks of methohexitol (frequency not defined but these complications are considered very rare since methohexitol is considered standard of care):

Sudden stop in blood circulation due to the failure of the heart, low blood pressure, shutdown of arteries and veins in the arms and legs, fast heart rate, agitation coming out of general anesthesia, headache, anxiety, restlessness, seizures, convulsion, injection site pain, abdominal pain, nausea or vomiting, blood clot in your leg that blocks one or more of your veins, breathing problems (stop breathing, bronchospasm, cough, labored breathing, hiccups, spasm of the vocal cords making it difficult to speak or breath, inadequate breathing).

One of three trained anesthesiologists will be administering each of these induction drugs, and has the expertise to anticipate and effectively treat each of these potential complications.

There is a possible risk of loss of confidentiality of health information.

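### Section 12.2 would judge methohexitol safer on hypotension and vasopressor use alone, while Section 8.3 plans no between-arm summary of adverse events or of removals for harm

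*Combined protocol and SAP*

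**What the plan says.** **The claim.** Section 12.2 plans to use the results to "determine whether methohexitol is a safer drug to use in anesthetic induction of patients receiving ACEI or ARBs (by causing less hypotension". The bracket is complete as "by causing less hypotension and less administration of vasopressor drugs". The section then says that such a finding may alter standard practice and improve patient safety.

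**The comparisons.** Section 8.3 compares the arms on:
- the proportion with hypotension and the proportion with refractory hypotension;
- counts of vasopressor doses and of hypotension episodes, and duration of hypotension;
- the areas under the curve (AUC) of systolic pressure, diastolic pressure and heart rate;
- the four neurohormones.

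**The harms the plan expects.** For propofol, Section 11.0 lists "abnormal heart rhythm (1% to 3%), slow or fast heart rate (1% to 3" per cent, among others. For methohexitol it lists fast heart rate, seizures, bronchospasm and vocal cord spasm. It gives no frequencies for these and regards them as very rare. Section 3.3.1 removes patients for "Unanticipated arrhythmia occurring during or immediately following anesthetic induction" and for "Unanticipated adverse effect of pre-induction drugs (lidocaine, fentanyl) or induction drugs (methohexitol or propofol" as named in its bracket.

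**What happens to those events.** Section 10.3 covers "Any adverse effects believed to be related to the administration of study drug", as judged by the anesthesiologist co-investigators; these effects "will be recorded on a case report form and submitted to the PI of the study within 24 hours of occurrence". Section 10.5 has them reviewed one case at a time. Section 10.7, on statistical tests, reads "Not applicable, due to the established safety of the study drugs compared to the study population size".

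**The concern.** The measures that define *safer* in Section 12.2 are those on which Section 1.1 already expects methohexitol to do better. Harms that could weigh the other way, or that could strengthen the case for methohexitol, are anticipated and at least partly recorded, but no planned result sets one arm beside the other. Improving how events are captured would not close this gap, because no planned comparison of adverse events would receive them.

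At stake is the interpretation. A statement meant to influence practice could be made without the reader seeing how many patients in each arm had an arrhythmia, an airway event or a drug reaction, or how many were taken off the protocol because of one.

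**Working it through.** **1. The plan's own figure.** Section 8.1 gives 47 per arm for 90% power to detect a difference of 0.30. The propofol rate is stated only as slightly above 0.82, so I assume 0.85 versus 0.55 (mean 0.70).

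n = [1.96·√(2·0.70·0.30) + 1.2816·√(0.85·0.15 + 0.55·0.45)]² / 0.30² = (1.2702 + 0.7848)² / 0.09 = 46.9, so 47.

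This reproduces the stated figure. With 20% drop-out, 47/0.80 = 58.75, so 59 per arm or 118 in all, against the stated 120. At the cited rates of 0.82 versus 0.52, n is 50 and 47 per arm gives power 0.884. The trial is sized for hypotension alone; the present point does not depend on this figure.

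**2. Following an adverse event through the plan.**

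| Step | Section | Arms compared? |
|---|---|---|
| Recorded if believed drug-related | 10.3 | No |
| Forms reviewed every 30 patients | 10.4 | No comparison specified |
| Relatedness and future conduct considered | 10.5 | No, case by case |
| Interim data | 10.2 | Limited to blood pressure, heart rate and vasopressors |
| Stop if one drug seems clearly more harmful | 11.0 | Implied, with no criterion or test |
| Final analysis | 8.3 | Adverse events and removals not named |
| Conclusion on *safer* | 12.2 | Hypotension and vasopressors only |

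Heart rate is the partial exception. It is measured each minute and compared by AUC, so a sustained shift in rate would show. A 15-minute AUC does not identify an arrhythmia, a seizure, bronchospasm or laryngospasm.

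**3. What 60 patients per arm can show.** Section 11.0 gives 1% to 3% for propofol arrhythmia. For methohexitol no rate is given, so nothing can be computed from the documents for that arm.

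- Chance of at least one event in 60 = 1 − (1 − r)^60: 0.45 at r = 1% and 0.84 at r = 3%.
- Two-sided exact 95% upper limit after 0/60 = 1 − 0.025^(1/60) = 6.0%. For 0/47 it is 1 − 0.025^(1/47) = 7.5%.
- Smallest split against zero with Fisher p < 0.05 at 60 per arm: 6 versus 0 (p = 0.027).
- Power = Φ{[d√n − 1.96√(2p̄q̄)] / √(p₁q₁ + p₂q₂)}, with assumed rates. For 3% versus 10%, (0.5422 − 0.6833)/0.3451 = −0.41, power 0.34. For 3% versus 20%, (1.3168 − 0.8843)/0.4349 = 0.99, power 0.84.

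Some events are therefore likely to be seen, formal testing would detect only large differences, and an arm with no events would not establish safety. Counts with intervals are the suitable summary.

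**The case against.** The strongest reply is that Section 12.2 is a statement of potential benefit and not a decision rule. It speaks of determining whether methohexitol is safer, and its bracket says what is meant. The hypothesis, aims and endpoints claim only hemodynamic and hormonal effects. This stands in part: a reader might infer that the protocol commits to an overall safety verdict, and the documents do not go that far. But Section 12.2 is where the plan says what the result is for, and it ties the word to changing practice.

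A reader might also infer that harm can have no influence at all. That is too strong. Section 10.5 lets adverse effects affect the conduct of the study, Section 10.4 has the forms analysed every 30 patients, and Section 11.0 speaks of stopping for comparative harm. These routes bear on conduct, not on the final comparison. Section 11.0 also sits badly with Section 10.8, which marks suspension as not applicable; the two must be reconciled, but that is a separate matter.

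Nor do the documents say that patients removed under Section 3.3.1 are counted as drop-outs. Section 8.3 keeps all randomised patients in the primary analyses by intention to treat. The 20% allowance (24 of 120) cannot be read as an expected number of harm-related removals: non-adherence is also a removal criterion, a difficult airway is not described as a drug harm, and lidocaine and fentanyl go to both arms. What remains is that intention to treat keeps the patient in the hypotension comparison without making the event that led to removal an outcome. Sections 3.3.2, 7.2.2 and 19.7 leave it unclear whether data collection continues for such patients.

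Two further points are fair. Section 8.3 promises frequencies and percentages for categorical variables, but does not name adverse events or removal reasons among them. Section 10.7 belongs to the monitoring plan, and its reliance on small numbers is a sound reason for not testing; it does not bar a descriptive final table.

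**Conclusion.** The point holds in a limited form. Section 12.2 ties *safer* to two outcomes, and Section 8.3 has no between-arm summary of adverse events or of removals for arrhythmia or induction-drug adverse effect. The existing reviews do not feed that conclusion.

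The primary estimate, the sample size and the type I error are untouched. The size of any imbalance in harms cannot be predicted from the documents, and none should be assumed. The 45% to 84% chance of seeing an event rests on the propofol arrhythmia rates in Section 11.0 applied to 60 patients. It says nothing about methohexitol or about the direction of a difference. The 6.0% upper limit after 0/60 shows why even an arm with no events would not support an unqualified claim. The change is worth making because it costs little and the claim is meant to influence practice.

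**What to change.** 1. **Section 8.3.** Add a descriptive safety table for all randomised patients by randomised arm. Give the number and percentage with each recorded adverse event and with each Section 3.3.1 removal reason. Include every recorded event, not only those judged related: Section 7.4.5 makes the trial open label, and co-investigators judge relatedness. Name *removed for arrhythmia or induction-drug adverse effect* as a safety outcome, with an exact 95% interval per arm and a 95% interval, by a method named in advance, for the difference. State that no powered test is planned.
2. **Section 12.2.** Limit the claim to less hypotension and less vasopressor use, and require any broader safety statement to be read alongside the table.
3. **Forms.** Record the removal reason, and record events whether or not they are judged related. Section 10.3 limits the form to related effects, whereas Section 19.1 defines adverse events regardless of relatedness and Section 20.1.2 speaks of all of them being entered, so the intended scope should be made explicit.

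The cost is a short paragraph, one table, a wording change and possibly one added form field, with no extra patients. The downsides are wide intervals for rare events and a narrower claim. No change to treatment or clinical management is involved.

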## **13.0 Sharing Results with Subjects**

The results of this study will not be shared with subjects.

## **14.0 Subject Stipend (Compensation) and/or Travel Reimbursements**

Not applicable

## **15.0 Economic Burden to Subjects**

### **15.1 Costs**

Not applicable

### **15.2 Compensation for research-related injury**

It is the policy of the institution to provide neither financial compensation nor free medical treatment for research-related injury. In the event of injury resulting from this research, medical treatment is available but will be provided at the usual charge. Costs for the treatment of research-related injuries will be charged to subjects or their insurance carriers.

## **16.0 Resources Available**

### **16.1 Facilities and locations**

Recruitment will take place at the Anesthesia Pre-Operative Clinic at the University Physicians Center of Penn State Hershey Medical Center. Administration of anesthesia and research-associated blood work will be obtained in the Penn State Hershey Medical Center operating suites. Blood samples will be stored and processed in the Biomedical Research Building in [name] laboratory.

### **16.2 Feasibility of recruiting the required number of subjects**

The number of potential subjects includes any patient seen at the Anesthesia Preoperative Clinic; this generally includes most patients undergoing elective surgical procedures. We estimate one year may be required in order to recruit and collect data from 120 patients.

### **16.3 PI Time devoted to conducting the research**

The PI has already been assigned devoted academic time by the department in order to pursue academic projects of his choosing. No additional academic time will be petitioned for on account of this project.

### **16.4 Availability of medical or psychological resources**

Not applicable

### **16.5 Process for informing Study Team**

Meetings will be held periodically as needed to ensure all research team members are informed about the protocol and their duties. Team emails will also be used to keep team members updated.

## **17.0 Other Approvals**

### **17.1 Other Approvals from External Entities**

Not applicable

### **17.2 Internal PSU Committee Approvals**

#### **Check all that apply:**

Anatomic Pathology – Hershey only – Research involves the collection of tissues or use of pathologic specimens. Upload a copy of the Use of Human Tissue For Research Form on the “Supporting Documents” page in CATS IRB. This form is available on the IRB website at:  
<http://www.pennstatehershey.org/web/irb/home/resources/forms>

Animal Care and Use – All campuses – Human research involves animals and humans or the use of human tissues in animals

Biosafety – All campuses – Research involves biohazardous materials (human biological specimens in a PSU research lab, biological toxins, carcinogens, infectious agents, recombinant viruses or DNA or gene therapy).

Conflict of Interest Review – All campuses – Research has one or more of study team members indicated as having a financial interest.

Radiation Safety – Hershey only – Research involves research-related radiation procedures. All research involving radiation procedures (standard of care and/or research-related) must upload the Radiation Review Form on the “Supporting Documents” page in CATS IRB. This form is available on the IRB website at: <http://www.pennstatehershey.org/web/irb/home/resources/forms>

IND/IDE Audit – All campuses – Research in which the PSU researcher holds the IND or IDE or intends to hold the IND or IDE.

Scientific Review – Hershey only – All investigator-written research studies requiring review by the convened IRB must provide documentation of scientific review with the IRB submission. The scientific review requirement may be fulfilled by one of the following: (1) external peer-review process; (2) department/institute scientific review committee; or (3) scientific review by the Clinical Research Center Advisory committee. NOTE: Review by the Penn State Hershey Cancer Institute Scientific Review Committee is required if the study involves cancer prevention studies or cancer patients, records and/or tissues. For more information about this requirement see the IRB website at: <http://www.pennstatehershey.org/web/irb/home/resources/investigator>

## 18.0 Multi-Site Research

Not applicable

## 19.0 Adverse Event Reporting

### 19.1 Adverse Event Definitions

For drug studies, incorporate the following definitions into the below responses, as written:	
Adverse event	Any untoward medical occurrence associated with the use of the drug in humans, whether or not considered drug related
Adverse reaction	Any adverse event caused by a drug
Suspected adverse reaction	Any adverse event for which there is a reasonable possibility that the drug caused the adverse event. Suspected adverse reaction implies a lesser degree of certainty about causality than “adverse reaction”. 
 
Reasonable possibility. For the purpose of IND safety reporting, “reasonable possibility” means there is evidence to suggest a causal relationship between the drug and the adverse event.
 

Serious adverse event or Serious suspected adverse reaction	Serious adverse event or Serious suspected adverse reaction: An adverse event or suspected adverse reaction that in the view of either the investigator or sponsor, it results in any of the following outcomes: Death, a life-threatening adverse event, inpatient hospitalization or prolongation of existing hospitalization, a persistent or significant incapacity or substantial disruption of the ability to conduct normal life functions, or a congenital anomaly/birth defect. Important medical events that may not result in death, be life-threatening, or require hospitalization may be considered serious when, based upon appropriate medical judgment, they may jeopardize the patient or subject and may require

	medical or surgical intervention to prevent one of the outcomes listed in this definition.
Life-threatening adverse event or life-threatening suspected adverse reaction	An adverse event or suspected adverse reaction is considered “life-threatening” if, in the view of either the Investigator (i.e., the study site principal investigator) or Sponsor, its occurrence places the patient or research subject at immediate risk of death. It does not include an adverse event or suspected adverse reaction that had it occurred in a more severe form, might have caused death.
Unexpected adverse event or Unexpected suspected adverse reaction.	An adverse event or suspected adverse reaction is considered “unexpected” if it is not listed in the investigator brochure, general investigational plan, clinical protocol, or elsewhere in the current IND application; or is not listed at the specificity or severity that has been previously observed and/or specified.

For device studies, incorporate the following definitions into the below responses, as written:	
Unanticipated adverse device effect	Any serious adverse effect on health or safety or any life-threatening problem or death caused by, or associated with, a device, if that effect, problem, or death was not previously identified in nature, severity, or degree of incidence in the investigational plan or IDE application (including a supplementary plan or application), or any other unanticipated serious problem associated with a device that relates to the rights, safety, or welfare of subjects.

## 19.2 Recording of Adverse Events

All adverse events (serious or non-serious) and abnormal test findings observed or reported to study team believed to be associated with the study drug(s) or device(s) will be followed until the event (or its sequelae) or the abnormal test finding resolves or stabilizes at a level acceptable to the investigator.

An abnormal test finding will be classified as an adverse event if one or more of the following criteria are met:

- The test finding is accompanied by clinical symptoms
- The test finding necessitates additional diagnostic evaluation(s) or medical/surgical intervention; including significant additional concomitant drug treatment or other therapy

**NOTE:** Simply repeating a test finding, in the absence of any of the other listed criteria, does not constitute an adverse event.

- The test finding leads to a change in study drug dosing or discontinuation of subject participation in the clinical research study
- The test finding is considered an adverse event by the investigator.

## 19.3 Causality and Severity Assessments

The investigator will promptly review documented adverse events and abnormal test findings to determine 1) if the abnormal test finding should be classified as an adverse event; 2) if there is a reasonable possibility that the adverse event was caused by the study drug(s) or device(s); and 3) if the adverse event meets the criteria for a serious adverse event.

If the investigator’s final determination of causality is “unknown and of questionable relationship to the study drug(s) or device(s)”, the adverse event will be classified as associated with the use of the study drug(s) or device(s) for reporting purposes. If the investigator’s final determination of causality is “unknown but not related to the study drug(s) or device(s)”, this determination and the rationale for the determination will be documented in the respective subject’s case history.

## **19.4 Reporting of Adverse Reactions and Unanticipated Problems to the FDA**

### **19.4.1 Written IND/IDE Safety Reports**

Not applicable

### **19.4.2 Telephoned IND Safety Reports – Fatal or Life-threatening Suspected Adverse Reactions**

Not applicable

## **19.5 Reporting Adverse Reactions and Unanticipated Problems to the Responsible IRB**

In accordance with applicable policies of The Pennsylvania State University Institutional Review Board (IRB), the investigator will report, to the IRB, any observed or reported harm (adverse event) experienced by a subject or other individual, which in the opinion of the investigator is determined to be (1) unexpected; and (2) probably related to the research procedures. Harms (adverse events) will be submitted to the IRB in accordance with the IRB policies and procedures.

## **19.6 Unblinding Procedures**

Not applicable

## **19.7 Stopping Rules**

While highly unlikely to occur, the study protocol will be terminated and the patient removed from the study if the protocol interferes in any way with providing safe anesthetic care for the patient, or if any part of the protocol cannot be completed as described above, for whatever the reason.

